7.2.4. Dose Adjustments, Delays, or Discontinuation from Study Drug

7.2.4.1. Galunisertib Dose Adjustments and Delays, Criteria for Resumption of Galunisertib Treatment, and Discontinuation for Phase 1b and 2

7.2.4.1.1. Galunisertib Dose Adjustments and Delays

During Phase 1b Cycles 1 and 2, no inpatient dose escalation or reduction of galunisertib is allowed. Subsequent cycles may be dose adjusted as outlined in Sections 7.2.4.1.2 and 7.2.4.2.

Table JBEF.7.1 summarizes dose adjustment for patients experiencing the following events that are considered possibly related to galunisertib during Phase 1b Cycle 3 and beyond and during Phase 2. Galunisertib will be omitted until the event resolves.

Table JBEF.7.1. Dose Adjustments for Galunisertib

Events Possibly Related to Galunisertib	Adjustment
ANC $<0.5 \times 10^9/L$ for longer than 7 days, or ANC $<1.0 \times 10^9/L$ with a single temperature of $>101^\circ F/38.3^\circ C$ or a sustained temperature of $>100.4^\circ F/38^\circ C$ for >1 hour	Galunisertib will be omitted until the event resolves. In Phase 1b, no dose reduction is permitted; in Phase 2, galunisertib should be reduced by 1 (Phase 1b) cohort dose level (see Table JBEF.6.1). If the event has not recovered by Day 1 of the subsequent cycle, then galunisertib should be permanently discontinued.
Platelet count $<25 \times 10^9/L$ or platelet count $<50 \times 10^9/L$ with bleeding	Galunisertib will be omitted until the event resolves. In Phase 1b, no dose reduction is permitted; in Phase 2, galunisertib should be reduced by 1 (Phase 1b) cohort dose level (see Table JBEF.6.1). If the event has not recovered by Day 1 of the subsequent cycle, then galunisertib should be permanently discontinued.
CTCAE Grade 3 or 4 nonhaematologic toxicity	Galunisertib will be omitted until the event resolves. In Phase 1b, no dose reduction is permitted; in Phase 2, galunisertib should be reduced by 1 (Phase 1b) cohort dose level (see Table JBEF.6.1). If the event has not recovered by Day 1 of the subsequent cycle, then galunisertib should be permanently discontinued.

Abbreviations: ANC = absolute neutrophil count; CTCAE = Common Terminology Criteria for Adverse Events.

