7.2.4.1.2. Criteria to Resume Treatment with Galunisertib

Patients may resume treatment with galunisertib when the drug-related AE(s) resolve(s) to Grade ≤ 1 or baseline, with the following exceptions:

- Nonhaematologic toxicity must resolve to CTCAE Grade 0, 1, or baseline level before resuming treatment (with the exception of alopecia, fatigue, skin rash, nausea, vomiting, constipation, or diarrhoea that can be controlled with treatment).
- Haematologic toxicity must resolve to a level that, in the opinion of the investigator, is reasonable to allow for continuation of treatment.
- Patients with baseline Grade 1 AST/ALT or total bilirubin who require dose delays for reasons other than a 2-grade shift in AST/ALT or total bilirubin may resume treatment in the presence of Grade 2 AST/ALT OR total bilirubin.

If dosing is delayed for galunisertib-related AEs such that the patient cannot resume galunisertib treatment by Day 1 of the next cycle, the patient should be withdrawn from galunisertib. At Cycle 3 and beyond in the Phase 1b part of the study, inpatient dose reduction is permitted for a DLT if a lower dose of galunisertib has been established to be safe in combination with nivolumab, the patient has recovered by Day 1 of the next cycle, and the patient, in the opinion of the investigator and the Lilly physician, is deriving benefit. In the Phase 2 part only, patients who do recover by Day 1 of the next cycle may have the dosage reduced to the next lower (Phase 1b) dose level (see [Table JBEF.6.1](#)). If the Phase 2 galunisertib dose is 50 mg QD, no dose reduction will be allowed.

If galunisertib dosing is omitted during the 14-day dosing period, dosing with galunisertib may resume within that same 14-day dosing period, to conclude as originally scheduled, if the patient has adequately recovered from the toxicity that required the galunisertib to be held. If the galunisertib cannot resume during that 14-day dosing period, it should continue to be held until Day 1 of the next cycle.

If both galunisertib (see directions above) and nivolumab (see directions in [Section 7.2.4.2.1](#)) are held, each drug may be resumed per the directions for each individual drug.

In case of a dose delay of galunisertib, patients can continue nivolumab treatment (at investigator discretion).

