7.2.4.1.3. Discontinuation from Galunisertib

If dosing is delayed for galunisertib-related AEs such that the patient cannot resume galunisertib treatment by Day 1 of the next cycle, the patient should be withdrawn from galunisertib. In the Phase 1b part, inpatient dose reduction is permitted for a DLT if a lower dose of galunisertib has been established to be safe in combination with nivolumab, the patient has recovered by Day 1 of the next cycle, and the patient, in the opinion of the investigator and the Lilly physician, is deriving benefit. In the Phase 2 part only, patients who do recover by Day 1 of the next cycle may have the dosage reduced to the next lower (Phase 1b) dose level (see [Table JBEF.6.1](#)). If the Phase 2 galunisertib dose is 50 mg QD, no dose reduction will be allowed. If in the investigator's opinion the toxicity is related to both study drugs, both drugs should be withheld.

If moderate or severe heart valve toxicities are observed or a patient develops an aneurysm, the patient must immediately be discontinued from galunisertib treatment (for definitions see [Attachment 10](#), including references on the ECHO assessment based on the Guidelines of the American and European Societies of Cardiac Echocardiography). These events will be considered serious AEs (SAEs) and should be reported to Lilly per standard SAE reporting requirements ([Table JBEF.8.1](#)). Exceptions to this rule must be approved by the ERBs and Lilly.

Patients with combined Grade 2 AST/ALT AND total bilirubin values meeting discontinuation parameters should have treatment permanently discontinued.

If a patient experiences an AE that requires the patient be discontinued from galunisertib, the patient should continue on nivolumab (if the patient has not previously met discontinuation criteria for nivolumab). If in the investigator's opinion the toxicity is related to both study drugs, both drugs should be held.

7.2.4.2. Nivolumab Dose Adjustments and Delays, Criteria for Resumption of Nivolumab Treatment, and Discontinuation in Phase 1b and 2

Inpatient dose escalations or reductions of nivolumab are not allowed in either Phase 1b or Phase 2.

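### For a listed toxicity still at Grade 3-4 on the next Day 1, Table JBEF.7.1 says stop galunisertib, while Section 7.2.4.1.2 sets no grade ceiling and can be read to allow restart

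*Protocol*

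**What the plan says.** Protocol Section 7.2.4.1.1 introduces Table JBEF.7.1 for events possibly related to galunisertib, in Phase 1b from Cycle 3 and throughout Phase 2. The third row covers Grade 3 or 4 nonhaematologic toxicity without naming any exception. Its hold rule is "Galunisertib will be omitted until the event resolves". Its stop rule is "If the event has not recovered by Day 1 of the subsequent cycle, then galunisertib should be permanently discontinued".

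Section 7.2.4.1.2 sets the criteria for resuming. Nonhaematologic toxicity has to return to Grade 0, 1 or baseline, "with the exception of alopecia, fatigue, skin rash, nausea, vomiting, constipation, or diarrhoea that can be controlled with treatment". No maximum grade is given for the events on that list.

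Sections 7.2.4.1.2 and 7.2.4.1.3 both carry a Day 1 withdrawal rule. It applies where "the patient cannot resume galunisertib treatment by Day 1 of the next cycle, the patient should be withdrawn from galunisertib".

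**The concern.** Take a patient with possibly galunisertib-related Grade 3 skin rash, held, and still Grade 3 on Day 1 of the next cycle. The table says galunisertib should end for good. The resumption section does not require rash to fall to Grade 1 and names no grade above which restart is barred. A site reading only that section could restart.

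This is a stopping rule in a trial whose Phase 2 primary objective is safety. It decides whether an investigational drug is given again during a persisting severe toxicity. If the Phase 2 dose turned out to be the lowest level, the restart would be at full dose: "If the Phase 2 galunisertib dose is 50 mg QD, no dose reduction will be allowed".

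**Working it through.** No arithmetic is needed to establish the conflict. The check sets the two texts side by side for a possibly galunisertib-related nonhaematologic event that reached Grade 3 or 4, assuming a baseline grade of 0 or 1.

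**1. Outcome on the next Day 1**

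| State on Day 1 | Table JBEF.7.1, row 3 | Section 7.2.4.1.2 | Agree? |
|---|---|---|---|
| Event not on the list, still Grade 3-4 | Stop | May not resume, so withdrawn | Yes |
| Listed event, back to Grade 0-1 | Recovered | May resume | Yes |
| Listed event, down to Grade 2 | Depends on the undefined term | Return to Grade 0-1 not required | Can be reconciled |
| Listed event, still Grade 3-4, controllable | Stop | Return to Grade 0-1 not required, no ceiling | No |
| Listed event, still Grade 3-4, not controllable | Stop | Depends on the qualifier (step 2) | Depends |

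**2. Reach of the control qualifier.** The closing words of the exemption can attach in three ways.
- To diarrhoea only: the other six events are exempt whether or not they are controlled.
- To the four gastrointestinal events: alopecia, fatigue and skin rash remain exempt without condition.
- To all seven: an uncontrolled event is not exempt and both texts stop galunisertib. What remains in conflict is a controllable event that persists at Grade 3-4.

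On none of the three is the qualifier a grade limit, so the fourth row of the table stays in conflict on every reading.

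**3. Does the Day 1 withdrawal rule settle it?** No. It is triggered by inability to resume. An exempt event does not by itself prevent resumption under 7.2.4.1.2, so the rule is not reached.

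**4. Does the word *recovered* settle it?** Section 7.2.4.1.2 uses the idea loosely. In Phase 2, "patients who do recover by Day 1 of the next cycle may have the dosage reduced to the next lower (Phase 1b) dose level". Within a dosing period, restart is allowed "if the patient has adequately recovered from the toxicity that required the galunisertib to be held". Both uses sit close to being fit to resume. If row 3 is read that way the texts agree, but that meaning is not written, and it would call an event recovered while it still meets row 3's own entry grade.

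**5. Does either text prevail?** Section 7.2.4.1.1 points later Phase 1b cycles to 7.2.4.1.2 and then gives the table. It states no order of precedence.

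**6. How the protocol handles grades elsewhere.** Section 7.2.4.2.2 lets nivolumab resume at Grade 2 fatigue, and at Grade 2 skin toxicity if there has been no Grade 3 skin event, but requires diarrhoea to return to baseline. The DLT definition in 7.2.2.1, by contrast, excepts controllable nausea, vomiting, diarrhoea and constipation, and some fatigue, from toxicity of Grade 3 or higher. A reader could carry either convention into 7.2.4.1.2.

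**The case against.** The best reply is that the texts can both be obeyed. The table says *should* and the resumption section says *may*, so a site that stops breaches neither. Section 7.2.4.1.2 lifts a requirement for listed events and never states that Grade 3 or 4 is acceptable. Read together, the table can be taken as the specific rule for Grade 3-4 and the exemption as relief for a residual Grade 2. This stands in part. A reader might infer that the protocol issues two opposed commands, or expressly authorises restart during severe toxicity. The documents support neither: the permission arises from a missing ceiling. But the reconciling reading is not written either, and the DLT definition gives a site some reason to think Grade 3 was meant.

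A second reply is that the sponsor may want controlled Grade 3 events to continue, so a Grade 2 limit is only a preference. That intention is possible, but then row 3 must say so. The limit is the option that keeps the stop rule already in row 3.

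A third reply is that the investigator can stop treatment for unacceptable toxicity under Section 6.3.2. That is true and lowers the practical risk. It does not tell two sites to act alike.

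**Conclusion.** The conflict is real but narrow. It concerns listed events persisting at Grade 3-4 on the next Day 1, in Phase 2 and in Phase 1b from Cycle 3. If the control qualifier covers all seven events, it is limited to controllable ones. Severity is low, and the wording should be corrected because it is a patient-safety stop rule.

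The number of patients is probably small, but that is a judgement, since the documents give no frequency for such events. A reader might go on to express the two readings as lost dose intensity or a shift in a cohort mean. The documents do not support such figures. Sections 6.2 and 7.2.1 leave treatment duration open, the six-cycle minimum in 6.2.2 yields to the discontinuation criteria, and SAP 6.9.1 leaves the exposure algorithms to the ADaM requirements. Nor does the point reach inference: the SAP 6.1.1 safety set needs only one dose of either drug, and alpha and power are untouched.

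The conclusion assumes that the event is judged possibly related to galunisertib. It covers the stop rule only, not the separate differences in dose-reduction wording between the table and the text.

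**What to change.** - In the 7.2.4.1.2 bullet, limit the exemption to listed events at Grade 2 or below.
- In row 3 of Table JBEF.7.1, define *recovered* as meeting the amended 7.2.4.1.2 criteria, so that a listed event still at Grade 3-4 on the next Day 1 ends galunisertib.
- State which events the control qualifier covers. Attaching it to nausea, vomiting, constipation and diarrhoea would match the DLT definition.

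This changes one table row and one bullet, with no added patients or procedures. The cost is that a few patients with a persistent but controlled Grade 3 listed event would stop galunisertib. Nivolumab then follows its own rules. Section 7.2.4.1.3 has it continue unless its discontinuation criteria are met or, in the investigator's opinion, "the toxicity is related to both study drugs, both drugs should be withheld". Section 7.2.4.2.3 generally ends nivolumab for a Grade 3 nonskin drug-related event lasting more than 7 days. In a 28-day cycle an event that is Grade 3 from Day 14 and still so on the next Day 1 (Day 29) has lasted 29 - 14 = 15 days. For nonskin events also attributed to nivolumab, that drug would therefore usually have ended already.

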7.2.4.1.2. Criteria to Resume Treatment with Galunisertib

Patients may resume treatment with galunisertib when the drug-related AE(s) resolve(s) to Grade ≤ 1 or baseline, with the following exceptions:

- Nonhaematologic toxicity must resolve to CTCAE Grade 0, 1, or baseline level before resuming treatment (with the exception of alopecia, fatigue, skin rash, nausea, vomiting, constipation, or diarrhoea that can be controlled with treatment).
- Haematologic toxicity must resolve to a level that, in the opinion of the investigator, is reasonable to allow for continuation of treatment.
- Patients with baseline Grade 1 AST/ALT or total bilirubin who require dose delays for reasons other than a 2-grade shift in AST/ALT or total bilirubin may resume treatment in the presence of Grade 2 AST/ALT OR total bilirubin.

If dosing is delayed for galunisertib-related AEs such that the patient cannot resume galunisertib treatment by Day 1 of the next cycle, the patient should be withdrawn from galunisertib. At Cycle 3 and beyond in the Phase 1b part of the study, inpatient dose reduction is permitted for a DLT if a lower dose of galunisertib has been established to be safe in combination with nivolumab, the patient has recovered by Day 1 of the next cycle, and the patient, in the opinion of the investigator and the Lilly physician, is deriving benefit. In the Phase 2 part only, patients who do recover by Day 1 of the next cycle may have the dosage reduced to the next lower (Phase 1b) dose level (see [Table JBEF.6.1](#)). If the Phase 2 galunisertib dose is 50 mg QD, no dose reduction will be allowed.

If galunisertib dosing is omitted during the 14-day dosing period, dosing with galunisertib may resume within that same 14-day dosing period, to conclude as originally scheduled, if the patient has adequately recovered from the toxicity that required the galunisertib to be held. If the galunisertib cannot resume during that 14-day dosing period, it should continue to be held until Day 1 of the next cycle.

If both galunisertib (see directions above) and nivolumab (see directions in [Section 7.2.4.2.1](#)) are held, each drug may be resumed per the directions for each individual drug.

In case of a dose delay of galunisertib, patients can continue nivolumab treatment (at investigator discretion).

No patient will have his/her galunisertib dose reduced more than once. Reescalation to the previous galunisertib dose is acceptable in the absence of continuing toxicities. If subsequent galunisertib dose reduction is required after reescalation, the patient must be maintained at the reduced dose level for all remaining cycles.

7.2.4.1.3. Discontinuation from Galunisertib

If dosing is delayed for galunisertib-related AEs such that the patient cannot resume galunisertib treatment by Day 1 of the next cycle, the patient should be withdrawn from galunisertib. In the Phase 1b part, inpatient dose reduction is permitted for a DLT if a lower dose of galunisertib has been established to be safe in combination with nivolumab, the patient has recovered by Day 1 of the next cycle, and the patient, in the opinion of the investigator and the Lilly physician, is deriving benefit. In the Phase 2 part only, patients who do recover by Day 1 of the next cycle may have the dosage reduced to the next lower (Phase 1b) dose level (see [Table JBEF.6.1](#)). If the Phase 2 galunisertib dose is 50 mg QD, no dose reduction will be allowed. If in the investigator's opinion the toxicity is related to both study drugs, both drugs should be withheld.

If moderate or severe heart valve toxicities are observed or a patient develops an aneurysm, the patient must immediately be discontinued from galunisertib treatment (for definitions see [Attachment 10](#), including references on the ECHO assessment based on the Guidelines of the American and European Societies of Cardiac Echocardiography). These events will be considered serious AEs (SAEs) and should be reported to Lilly per standard SAE reporting requirements ([Table JBEF.8.1](#)). Exceptions to this rule must be approved by the ERBs and Lilly.

Patients with combined Grade 2 AST/ALT AND total bilirubin values meeting discontinuation parameters should have treatment permanently discontinued.

If a patient experiences an AE that requires the patient be discontinued from galunisertib, the patient should continue on nivolumab (if the patient has not previously met discontinuation criteria for nivolumab). If in the investigator's opinion the toxicity is related to both study drugs, both drugs should be held.

7.2.4.2. Nivolumab Dose Adjustments and Delays, Criteria for Resumption of Nivolumab Treatment, and Discontinuation in Phase 1b and 2

Inpatient dose escalations or reductions of nivolumab are not allowed in either Phase 1b or Phase 2.

7.2.4.2.1. Nivolumab Dose Adjustments and Delays

Dose delay criteria specified below apply for all nivolumab-related AEs. Nivolumab must be delayed until treatment can resume. There will be no dose reductions for nivolumab.

Nivolumab administration should be delayed for the following:

- Any Grade ≥ 2 nonskin, drug-related AE, with the following exceptions:
 - Grade 2 drug-related fatigue or laboratory abnormalities do not require a treatment delay
- Any Grade 3 skin, drug-related AE
- Any Grade 3 drug-related laboratory abnormality, with the following exceptions for asymptomatic amylase or lipase, AST, ALT, or total bilirubin:
 - Grade 3 amylase or lipase abnormalities that are not associated with symptoms or clinical manifestations of pancreatitis do not require a dose delay. It is recommended to consult with the Lilly CRP for Grade 3 amylase or lipase abnormalities, and to assess clinically relevant laboratory tests at more frequent intervals which will be determined by the investigator.
 - If a patient has a baseline AST, ALT, or total bilirubin that is within normal limits, delay dosing for drug-related Grade ≥ 2 toxicity
 - If a patient has baseline AST, ALT, or total bilirubin within the Grade 1 toxicity range, delay dosing for drug-related Grade ≥ 3 toxicity
 - For HCC patients only, if a patient has baseline AST, ALT, or total bilirubin within the Grade 2 toxicity range, delay dosing if these become 2x baseline levels during the study.
- Any AE, laboratory abnormality, or intercurrent illness which, in the judgement of the investigator, warrants delaying the dose of study medication

If nivolumab dosing is omitted on Days 1 or 15 of a cycle, dosing with nivolumab will be resumed 14 days later (next scheduled dose) as per the original schedule if the patient has

adequately recovered from the toxicity that required the nivolumab to be held. If the nivolumab cannot be resumed on the following Day 1 or 15, it should continue to be held until the next Day 1 or 15. Galunisertib should continue as scheduled.

If both galunisertib (see directions in Section 7.2.4.1.1) and nivolumab (see directions above) are held, each drug may be resumed per the directions for each individual drug.

7.2.4.2.2. Criteria for Resumption of Nivolumab Treatment

Patients may resume treatment with nivolumab when the drug-related AE(s) resolve(s) to Grade \leq 1 or baseline, with the following exceptions:

- Patients may resume treatment in the presence of Grade 2 fatigue
- Patients who have not experienced a Grade 3 drug-related skin AE may resume treatment in the presence of Grade 2 skin toxicity
- Patients with baseline Grade 1 AST/ALT or total bilirubin who require dose delays for reasons other than a 2-grade shift in AST/ALT or total bilirubin may resume treatment in the presence of Grade 2 AST/ALT OR total bilirubin
- Drug-related pulmonary toxicity, diarrhoea, or colitis must have resolved to baseline before treatment is resumed. Patients with persistent Grade 1 pneumonitis after completion of a steroid taper over at least 1 month may be eligible for retreatment if discussed with and approved by the Lilly CRP
- Drug-related endocrinopathies adequately controlled with only physiologic hormone replacement may resume treatment after consultation with the Lilly CRP

Dose delay of nivolumab which results in treatment interruption of >6 weeks require treatment discontinuation, with exceptions as noted above.

7.2.4.2.3. Discontinuation from Nivolumab

Nivolumab treatment should be permanently discontinued for the following:

- any Grade 2 drug-related uveitis, eye pain or blurred vision that does not respond to topical therapy and does not improve to Grade 1 severity within the retreatment period OR requires systemic treatment
- any Grade 3 nonskin, drug-related AE lasting >7 days, with the following exceptions for laboratory abnormalities, drug-related uveitis, pneumonitis, bronchospasm, hypersensitivity reactions, infusion reactions, and endocrinopathies:
 - Grade 3 drug-related uveitis, pneumonitis, bronchospasm, hypersensitivity reaction, or infusion reaction of any duration requires discontinuation
 - Grade 3 drug-related endocrinopathies adequately controlled with only physiologic hormone replacement do not require discontinuation
 - Grade 3 drug-related laboratory abnormalities do not require treatment discontinuation except:
 - Grade 3 drug-related thrombocytopenia >7 days or associated with bleeding requires discontinuation

- any drug-related liver function test abnormality that meets the following criteria require discontinuation:
 - AST or ALT >8xULN
 - total bilirubin >5xULN
 - concurrent AST or ALT >3xULN and total bilirubin >2xULN
 - for HCC patients only:
 - AST or ALT >10xULN for >2 weeks
 - AST or ALT >15xULN irrespective of duration
 - Total bilirubin >8xULN irrespective of duration for patients with elevated bilirubin at study entry or >5xULN for those with normal total bilirubin at entry
 - Concurrent AST or ALT >3xULN and total bilirubin >5xULN for patients entering treatment with a normal bilirubin and up to 8xULN for patients with elevated bilirubin
- Patients with combined Grade 2 AST/ALT AND total bilirubin values meeting discontinuation parameters should have treatment permanently discontinued.
- any Grade 4 drug-related AE or laboratory abnormality, except for the following events which do not require discontinuation:
 - Grade 4 neutropenia ≤7 days
 - Grade 4 lymphopenia or leukopenia
 - isolated Grade 4 amylase or lipase abnormalities that are not associated with symptoms or clinical manifestations of pancreatitis. The Lilly CRP should be consulted for Grade 4 amylase or lipase abnormalities.
 - isolated Grade 4 electrolyte imbalances/abnormalities that are not associated with clinical sequelae and are corrected with supplementation/appropriate management within 72 hours of their onset
 - Grade 4 drug-related endocrinopathy AEs (such as adrenal insufficiency, adrenocorticotropic hormone deficiency, hyperthyroidism or hypothyroidism, or glucose intolerance) which resolve or are adequately controlled with physiologic hormone replacement (corticosteroids, thyroid hormones) or glucose-controlling agents, respectively, may not require discontinuation after discussion with and approval from the Lilly CRP
- any event that leads to delay in dosing lasting >6 weeks from the previous dose requires discontinuation, with the following exceptions:
 - *Dosing delays to allow for prolonged steroid tapers to manage drug-related AEs are allowed. Prior to reinitiating treatment in a patient with a dosing delay lasting >6 weeks from the previous dose, the Lilly CRP must be consulted. Tumour assessments should continue as per protocol even if dosing is delayed. Periodic study visits to assess safety and laboratory studies should also continue every 6 weeks or more frequently if clinically indicated during such dosing delays.*
 - *Dosing delays lasting >6 weeks from the previous dose that occur for non-drug-related reasons may be allowed if approved by the Lilly CRP. Prior to reinitiating treatment in a patient with a dosing delay lasting >6 weeks, the Lilly CRP must be consulted. Tumour assessments should continue as per protocol even if*

dosing is delayed. Periodic study visits to assess safety and laboratory studies should also continue every 6 weeks or more frequently if clinically indicated during such dosing delays.

- any AE, laboratory abnormality, or intercurrent illness which, in the judgement of the investigator, presents a substantial clinical risk to the patient with continued nivolumab dosing

If a patient experiences an AE that requires the patient be discontinued from nivolumab, the patient should continue on galunisertib (if the patient has not previously met discontinuation criteria for galunisertib). If in the investigator's opinion the toxicity is related to both study drugs, both drugs should be held.

